5. STUDY PROCEDURES

5.1 Study Visits

For each subject the duration of the study will not exceed 5 years and 6 months post imlifidase dosing.

All subjects considered for the study must be informed about the study, verbally and in writing, and give their written consent before any study procedure is performed. After informed consent is obtained, pre-study visit data such as information on graft survival and patient survival can be collected and entered in the CRF.

Some subjects will not perform all 4 visits because the study start will be after the subjects' first visit should have taken place.

If a subject is not able to attend a planned visit at the site, the visit can be performed remotely. The blood sampling should be performed at the local laboratory (if possible) and QOL forms

sent to the subject. The following activities and assessments will be performed at **1 year** (+/- 2 months), **2 years** (+/- 4 months), **3 years** (+/- 4 months) and **5 years** (+/- 6 months) **post imlifidase dosing:**

- Check of inclusion and exclusion criteria will be performed at the first visit for each subject after 1, 2 or 3 years post imlifidase dosing.
- Subjects shall complete QoL questionnaires (EQ-5D-5Land KDQOL-SF)
- Evaluation of graft survival
- Record patient survival (if applicable, date and cause of death)
- Safety laboratory tests (see Table 3)
- P-creatinine, eGFR and U-proteinuria tests
- DSA samples
- ADA sample
- BK virus sample
- Record comorbidity such as infections, malignancy, diabetes mellitus and cardiovascular events
- Record graft rejection episodes (classified by Banff)
- If applicable, record information from standard of care kidney biopsy reports
- Record treatments of graft rejection episodes (PE, IVIg, dialysis, other)
- Record current immunosuppressive medication
- Record and report AEs caused by study procedure or a clinically significant safety lab value

5.2 Flow Chart

Table 2. Study flow chart.

Visit post imlifidase dosing	1 year ¹	2 years	3 years	5 years
Visit window	(+/- 2 months)	(+/- 4 months)	(+/- 4 months)	(+/- 6 months)
Informed consent	x ²			
Eligibility	x ²			
Enrollment and allocation of patient number	x ²			
QoL questionnaires (EQ-5D-5L, KDQOL-SF)	x	x	x	x
Patient survival status	x ³	x	x	x
Graft survival status	x ³	x	x	x
Graft rejection episodes ⁴	x	x	x	x
Kidney biopsy reports ⁵	x	x	x	x
P-creatinine, eGFR calculation (performed by Sponsor)	x	x	x	x
Proteinuria (dipstick)	x	x	x	x
Hematology (Hemoglobin, Diff of leukocytes, Thrombocytes)	x	x	x	x
Total IgG	x	x	x	x
BK test	x	x	x	x
DSA (HLA antibody, Luminex) central lab	x	x	x	x
DSA (HLA antibody, Luminex) local lab	x	x	x	x
ADA (Anti-imlifidase IgG) central lab	x	x	x	x
Comorbidity ⁶	x	x	x	x
Current immunosuppressive medication	x	x	x	x
Treatment of graft rejection episode (PE, IVIg, dialysis, other)	x	x	x	x
Adverse events ⁷	x	x	x	x

¹. Some subjects will not perform all 4 visits because the study start will be after the subject's first visit should have taken place. If applicable, record creatinine and proteinuria results from planned time for 1- and 2 Years visits. End of Study (EOS) will occur 5 years (+/- 6M) after transplantation or earlier in the case of death, withdrawal of consent or lost to follow up.

². These activities shall be performed at subject's first visit that can take place 1, 2, or 3 years post imlifidase dose depending on when the subject was transplanted in the feeder study.

³. After informed consent is obtained, pre-study visit data such as information on graft survival and patient survival can be collected and entered in the CRF. If applicable, record cause and date of death.

⁴. Record biopsy proven graft rejection episodes (classified by the Banff classification) and creatinine and proteinuria results from the episode.

⁵. If standard of care kidney biopsies are performed for any reason, at any time-point, e.g. suspected rejections, record information in the CRF.

⁶. Record comorbidities that are medically relevant and registered in the subject's medical record. Medically relevant comorbidity are infections, malignancy, diabetes mellitus and cardiovascular events.

⁷. Adverse events caused by a procedure in the protocol (blood sampling) or a clinically significant safety lab value are the only AEs that will be captured and reported. If the lab value is attributable to worsening renal function, graft rejection or natural progression of disease, it will not be reported as AE

6. STUDY ASSESSMENTS

6.1 Assessments related to Primary Endpoint

The time points for all study assessments are shown in the study flow chart ([Table 2](#)). Laboratory sampling, shipment, and analysis will be described in detail in the laboratory manual.

6.1.1 Graft Survival

The primary endpoint of this study is to determine overall graft survival, defined as time from transplantation to graft loss. Graft loss is defined as permanent return to dialysis for at least 6 weeks, re-transplantation, or nephrectomy. If dialysis is used to define graft loss, the date of graft loss will be the first day of the last ongoing dialysis period reported.

6.2 Assessments related to Secondary Endpoints

6.2.1 Patient survival

Overall patient survival is defined as time from transplantation to death for any cause. If applicable, information on time and cause of death will be recorded.

6.2.2 Kidney function

Kidney function will be evaluated by P-creatinine and calculation of estimated filtration rate (eGFR) by MDRD/CKD-EPI formula (performed by Sponsor). Proteinuria will be measured by dipstick. The samples will be taken at the time points presented in the study flow chart. Creatinine and proteinuria results from graft rejection episodes will be collected as well as from the time for planned 1- and 2-years visit if study start was after those visits should have taken place.

6.2.3 Kidney biopsy

If standard of care kidney biopsies are performed for any reason, at any time-point, e.g. suspected rejections, information will be collected and recorded in the CRF.

6.2.4 Graft rejection episodes

Information about the occurrence of graft rejection episodes will be collected, following Banff classification.

6.2.5 Treatment of graft rejection episodes

Information about treatments of graft rejection episodes will be recorded (e.g dialysis, plasmapheresis and medications).

6.2.6 Comorbidity

Information about comorbidities that are medically relevant and registered in the subjects' medical record will be collected. Medically relevant comorbidity are e.g. infections, malignancy, diabetes mellitus and cardiovascular events.

6.2.7 Donor Specific Antibodies (DSA)

Samples for determination of DSAs will be analysed in LABScreen single antigen HLA class I and class II assays. The assays allow determination of the mean fluorescence intensity (MFI) of antibodies in patient serum reacting to an array of individual HLA immobilized to beads. Analyses of DSAs will be performed centrally, at Hansa Biopharma, Lund. The date and time of collection of each sample will be recorded on the sample log and in the CRF.

Samples for DSA will also be analysed by the hospital laboratory and the results will be evaluated by the Investigator and recorded in the CRF.

6.2.8 Immunogenicity by Anti-Drug Antibodies (ADA)

Samples for the determination of anti-drug antibody (ADA) levels in serum will be analysed for anti-imlifidase IgG using a customized imlifidase ImmunoCAP test. The analysis will be performed at the central laboratory, ThermoFisher Scientific, Immuno Diagnostics, Service Laboratory, Allerød, Denmark. Full details of the analytical method used, and the analysis results will be detailed in a separate bioanalytical report. The ADA samples will be taken at the times presented in the study flow chart. The date and time of collection of each sample will be recorded on the laboratory requisition form and in the CRF.

6.2.9 Health Related Quality of Life Questionnaire (HR-QoL)

At all visits, two patient questionnaires will be used to assess health related quality of life. European Quality of Life-5 levels (EQ-5D-5L) and Kidney Disease Quality of Life Questionnaire-short form (KDQOL-SF). The individual guidelines for the questionnaires will be followed when administering the forms.

6.3 Safety and other Laboratory Samples

The investigator will review the laboratory results and evaluate and document whether the results are normal or abnormal and whether abnormal results are clinically or non-clinically significant. The local hospital laboratory will be used for the analyses and updated laboratory certificate and reference ranges will be collected. The samples will be taken at the times presented in the study flow chart (Table 2). The safety hematology and clinical chemistry tests will be the following:

Table 3. Safety hematology and clinical chemistry laboratory tests

Hematology¹⁾
B-Hemoglobin
B-Differential analysis of leucocytes
B-Thrombocytes
Clinical Chemistry
P-IgG

¹⁾ May be taken as serum samples if that is standard procedure at local lab

Virology test for BK will also be taken at the local hospital laboratory.

7. BIOLOGICAL SAMPLING PROCEDURES

7.1 Handling, Storage and Destruction of Biological Samples

Details on handling of biological samples will be described in the laboratory manual that will be provided to the center prior to inclusion of the first patient.

ADA and DSA samples may be stored for maximum 2 years after completion of the study report according to local regulations.

Analyses cannot be used or re-used for purposes different from the ones stated in the protocol. Analyses not described in this protocol can only be performed after obtaining the required approvals and new written informed consent.

7.2 Chain of Custody of Biological Samples

A full chain of custody is maintained for all samples throughout their life cycle.

The principal investigator keeps full traceability of collected biological samples from the patients while in storage at the centre until shipment and keeps documentation of receipt of arrival.

The sample receiver keeps full traceability of the samples while in storage and during use until used or disposed.

Hansa Biopharma keeps oversight of the entire life cycle through internal procedures, monitoring of study sites and auditing of external laboratory providers.

7.3 Withdrawal of Informed Consent for Donated Biological Samples

If a subject withdraws consent to the use of biological samples donated the samples will be disposed/destroyed, if not already analysed and documented.

The principal investigator:

- will ensure that subject withdrawal of informed consent is notified immediately to Hansa Medical
- will ensure that biological samples from that subject, if stored at the study site, are immediately identified, disposed/destructed and the action documented.
- will ensure the laboratory(ies) holding the samples is/are informed about the withdrawn consent immediately and that samples are disposed/destructed, and the action documented returned to the study site.

Hansa Biopharma ensures the laboratory(ies) holding the samples is/are informed about the withdrawn consent immediately and that samples are disposed/destructed, and the action documented returned to the study site.

In the event that analysis/research has already been performed, Hansa Biopharma will retain the results and associated data for regulatory reasons, but these will not be used in any subsequent analyses.

8. ADVERSE EVENTS AND SERIOUS ADVERSE EVENTS

8.1 Definitions

8.1.1 Adverse event

An adverse event (AE) is the development of an undesirable medical condition or the deterioration of a pre-existing medical condition following or during exposure to a pharmaceutical product, whether or not considered causally related to the product. Relationship to the study drug will be deemed as not related, unlikely, possible or probable. An undesirable medical condition can be symptoms (e.g., nausea and chest pain), signs (e.g., tachycardia and enlarged liver) or the abnormal results of an investigation (e.g., laboratory findings and electrocardiograms).

In cases of surgical or diagnostic procedures, the condition/illness leading to such a procedure is considered as the AE rather than the procedure itself.

In case of a fatality, the cause of death is considered as the AE, and the death is considered as its outcome.

8.1.2 Serious adverse event

A serious adverse event (SAE) is an AE or suspected adverse reaction (SAR) that is considered "serious" if, in the view of either the investigator or Hansa Biopharma, it results in any of the following outcomes:

- Results in death
- Is immediately life-threatening

- Requires in-patient hospitalisation or prolongation of existing hospitalisation.
- Results in persistent or significant disability or incapacity
- Is a congenital abnormality or birth defect
- Is an important medical event that may jeopardise the subject or may require medical intervention to prevent one of the outcomes listed above.

Life-threatening event: An adverse event or suspected adverse reaction is considered "life-threatening" if, in the view of either the investigator or Hansa Biopharma, its occurrence places the patient or subject at immediate risk of death. It does not include an adverse event or suspected adverse reaction that, had it occurred in a more severe form, might have caused death.

Disability is defined as a substantial disruption in a person's ability to conduct normal life functions.

Hospitalisation: Admittance to an emergency room for observation without being admitted to the hospital may be considered to be an AE but is not considered as an SAE. However, complications that occur during hospitalization are AEs, and if a complication prolongs hospitalization, the event is considered serious.

8.2 Collection and Recording of Adverse Events

In clinical studies, an AE/SAE can occur at any time after signing of the informed consent until the end of the study, including run-in or washout periods, even if no study treatment has been administered, e.g., an AE can be related to a procedure in the protocol.

AEs will therefore be collected on the AE CRF according to the information in [section 8.3](#).

8.2.1 Variables

The following variables will be recorded in the CRF for each AE; description of the AE, the date and time (if applicable) when the AE started and stopped, severity based on Common Terminology Criteria for Adverse Events grading (CTCAE v.4.03) whether the AE is serious or not, causality rating, action taken, and outcome.

8.2.1.1 Causality assessment

For each reported AE the investigator will assess the relationship of the event to study procedures using the following criteria:

- **Unrelated:** applicable to an AE that occurs when the subject was not exposed to study treatment or another cause is obvious (e.g. if a lab abnormality is unrelated to the study procedure the investigator would tick the 'unrelated' box, and then specify as to what they consider the lab abnormality was related to).
- **Related:** applicable to AEs where there is a connection with study procedures.

For SAEs, causal relationship will also be assessed for any study procedure.

8.2.2 Adverse Events Based on Signs and Symptoms

When collecting AEs, the recording of diagnoses is preferred (when possible) rather than recording a list of signs and symptoms, for example: congestive heart failure rather than low ejection fraction, rales and dyspnea. However, if a diagnosis is known and there are other signs or symptoms that are not generally part of the diagnosis, the diagnosis and each sign or symptom not part of the diagnosis will be recorded separately, for example: congestive heart failure and conjunctivitis.

8.2.3 Adverse Events Based on Examinations and Tests

If safety lab values are judged as clinically significant, they will be captured as AEs and if SAE criteria is fulfilled they will also be SAEs.

Wherever possible the reporting investigator uses the clinical, rather than the laboratory term (e.g., anaemia *versus* low haemoglobin value).

8.2.4 Follow up of Unresolved Adverse Events

Any AEs that are unresolved at the subject's last AE assessment in the study are followed up by the investigator until stabilization, for as long as medically indicated or the overall clinical outcome of the subject is known, unless the subject is documented as "lost to follow up". All SAEs and AEs leading to discontinuation should be followed until the event resolves, stabilizes, or returns to baseline.

Reasonable attempts to obtain this information must be made and documented. Hansa Biopharma retains the right to request additional information for any subject with ongoing AE(s)/SAE(s) at the end of the study, if judged necessary.

8.2.5 Reporting of Serious Adverse Events

All SAEs have to be reported, whether or not considered related to the investigational product, or to the study procedure(s), on a separate SAE form. In the Adverse Event form, it will be added that the AE is considered serious. SAEs will be recorded from the time of informed consent.

An assigned contract research organisation (Primevigilance) will be responsible for reporting all SAEs to Regulatory Authorities (RA) in accordance with International Conference on Harmonisation [\(ICH\)](#), Good Clinical Practice (GCP) [\(GCP\)](#) and local regulations.

As soon as the Investigator is aware of a potential SAE he/she should contact Primevigilance by e-mail no later than 24 hours after the knowledge of such a case. At the time of initial reporting the investigator must provide as a minimum requirement, subject number, birth date, description of the SAE and a preliminary assessment of causality.

Contact Information:

CRO: **Primevigilance**
e-mail: [REDACTED]

For fatal or life-threatening adverse events where important or relevant information is missing, active follow up is undertaken immediately. Investigators or other site personnel inform Hansa Biopharma and monitor of any follow up information on a previously reported SAE immediately but no later than within 24 hours of when he or she becomes aware of it. The monitor or Hansa Biopharma will advise the investigator/study site personnel how to proceed.

The SAE reporting procedures are detailed in the study specific Safety Management Plan. This plan is an agreement between the Hansa Biopharma, and Primevigilance.

8.2.6 Reporting of Suspected Unexpected Serious Adverse Reactions (SUSARs)

Suspected Unexpected Serious Adverse Reactions (SUSARs) must be reported to RAs. A suspected serious adverse reaction is any SAE for which there is a reasonable possibility that the investigational product caused the adverse event. A serious adverse reaction is considered "unexpected" if it is not listed in the reference safety information section of the investigator brochure or is not listed at the specificity or severity that has been observed.

SUSARs with an outcome of death or which are life threatening must be reported to the relevant RAs within 7 calendar days, all other SUSARs must be submitted within 15 calendar days. The SUSAR reporting procedures are detailed in the study Safety Management Plan. This plan is an agreement between the Hansa Biopharma, and Primevigilance. Hansa Biopharma will notify the appropriate RA(s) and all participating study investigators of any SUSARs on an expedited basis and in accordance with applicable regulations. In addition, Hansa Biopharma is responsible for informing all investigators in all other ongoing studies involving imlifidase about all SUSARs.

It is the responsibility of the site investigator to promptly notify the Independent Ethics Committee (IEC) and other appropriate institutional regulatory bodies of all SUSARs received involving risk to human subjects as per their applicable requirements

8.3 Adverse Events of Special Interest

Adverse events caused by a procedure in the protocol (such as blood sampling) or a clinically significant safety lab value are the only AEs that will be captured and reported in the study. If the lab value is attributable to worsening renal function, rejection, or natural progression of disease, it will not be reported as AE.

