8.4 Pregnancy and Pregnancy Outcome

Pregnancy was an exclusion criterion in the feeder studies and a pregnancy test was performed at the screening visit in each study. No pregnancies were reported during the clinical studies.

If a subject becomes pregnant during the current study, the subject will continue in the study according to study protocol, if possible. A Pregnancy Report Form must be sent by the investigator to Primevigilance at the latest within two weeks of learning of the pregnancy. The outcome of all pregnancies (spontaneous miscarriage, elective termination, normal birth or congenital abnormality) will be followed up on the Pregnancy Report Form even after the subject has completed or discontinued the study. Primevigilance will follow up on pregnancy outcome 4 weeks after the projected due date.

Pregnancy itself is not considered an AE or SAE, but any event occurring during pregnancy that meets serious criteria must be reported to Hansa Biopharma and will be handled as a SAE. Spontaneous abortions, congenital abnormalities/birth defects are always considered to be SAEs and will be reported and followed up in accordance with other SAEs. Any SAE occurring as a result of a post-study pregnancy and considered reasonably related to the study drug by the investigator will be reported to HansaBiopharma (or designee).

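### Protocol 8.2.5 requires every SAE to be reported, but 8.3 and its parallels limit AE capture to procedure- or safety-lab-related events with no SAE exception, so any AE-based output may omit serious events

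*Protocol*

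**What the plan says.** **The wide rule.** Protocol 8.2.5 states: "All SAEs have to be reported, whether or not considered related to the investigational product, or to the study procedure(s". Recording starts at informed consent and uses a separate SAE form. The AE form is also involved: "In the Adverse Event form, it will be added that the AE is considered serious". Section 8.4 extends this to pregnancy: "any event occurring during pregnancy that meets serious criteria must be reported to Hansa Biopharma and will be handled as a SAE". It adds: "Spontaneous abortions, congenital abnormalities/birth defects are always considered to be SAEs".

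**The narrow rule.** Protocol 8.3 says that procedure-caused events or clinically significant safety lab values "are the only AEs that will be captured and reported in the study", and then removes lab values attributable to worsening renal function, rejection or natural disease progression. Footnote 7 to the flow chart in 5.2 repeats the limit: "Adverse events caused by a procedure in the protocol (blood sampling) or a clinically significant safety lab value are the only AEs". The visit list in 5.1 and the analysis text in 11.7.1 carry the same scope. Section 8.2 routes the AE form to it: "AEs will therefore be collected on the AE CRF according to the information in" section 8.3.

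**The SAP.** SAP 2.1 copies footnote 7. SAP 4.5.1 then presents all recorded AEs in an overview table with rows for all AEs, deaths, SAEs, AEs leading to withdrawal, and severe and life-threatening AEs. It also plans a table by SOC and PT, and listings that include SAEs and AEs leading to death. It does not say which capture rule those rows reflect.

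**The concern.** A site that follows 8.2.5 enters an unrelated hospitalisation or death as a serious AE. A site that follows 8.3 does not. Serious events could therefore be present or absent according to which section a site worked from, and nothing in the planned output would show it.

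Two misreadings could follow. A low SAE count could mean few serious events or narrow capture. The Deaths row of the AE overview could show 0 while the patient survival table in the same report shows deaths. In a long-term follow-up study meant to inform future prescribers and patients, readers should not have to guess which explanation applies.

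**Working it through.** No arithmetic produces or tests this point, so the check compares the texts and then traces the outputs.

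**Step 1: do the definitions keep the two rules apart?** No. Protocol 8.1.2 defines an SAE as an AE or suspected adverse reaction that meets a seriousness criterion. Section 8.1.1 makes the cause of a death the AE, with death as its outcome. A limit on AEs therefore also limits SAEs unless an exception is written, and none is.

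**Step 2: pass sample events after consent through both rules.**

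| Event | 8.2.5 and 8.4 | 8.3, 5.1, footnote 7, 11.7.1 |
|---|---|---|
| Hospitalisation for infection, not caused by a procedure and not a safety lab value | SAE, reported and flagged on the AE form | Not captured as an AE |
| Death from malignancy | SAE, reported and flagged on the AE form | Not captured as an AE |
| Spontaneous abortion | Always an SAE | Not captured as an AE |
| Clinically significant haemoglobin value that meets a seriousness criterion and has none of the excluded causes | SAE, reported | Captured |

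The rules agree only on the last row. The safety lab tests named in Table 3 are haemoglobin, leucocyte differential, thrombocytes and P-IgG. The lab route into the narrow rule is therefore small, although BK testing appears under the same heading in 6.3 and its status as a safety lab value is not stated.

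**Step 3: trace an uncaptured SAE through the planned outputs (SAP 4.5.1, 9.1, 9.2).**

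- Table 14.3.16 has 5 rows. The event is always missing from 2 (all AEs, SAEs). Depending on the event, it is also missing from the other 3 (deaths, withdrawal, severe and life-threatening).
- Table 14.3.17 (SOC and PT): always missing.
- Listings 16.3.1, 16.3.2 and 16.3.3: always missing. Listing 16.3.4: missing if the event was fatal. Listing 16.3.5: missing if it led to withdrawal.

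That is 2 tables + 5 listings = 7 outputs, of which 2 + 3 = 5 are always incomplete and 2 depend on the event.

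**Step 4: is there another route into these outputs?** SAP 2.4 names the data management database, central laboratory files and a sponsor file of rejection episodes from the feeder studies. It names no transfer of SAE reports from the safety CRO.

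**Step 5: what is recorded elsewhere?** Date and cause of death are recorded at each visit (Protocol 5.1, 6.2.1) and reported as all-cause survival in Table 14.2.3 and Listing 16.2.6.6. Infections, malignancy, diabetes and cardiovascular events are recorded as comorbidity (6.2.6) and tabulated by type (SAP 4.4.2). Rejection, its treatment and graft loss have their own outputs.

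**Step 6: size.** The documents give no SAE, hospitalisation or death rate, so the number of affected events cannot be derived. The only bound is the population of at most 46 subjects.

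**The case against.** The best defence is that 8.2.5 gives only the reporting route for serious events already inside the 8.3 set. Several passages support this. SAEs are defined as a kind of AE. Section 8.2, which contains 8.2.5, sends AE collection to 8.3. Section 8.2.3 describes how a clinically significant safety lab value becomes an AE and then, if criteria are met, an SAE. The instruction to mark the AE as serious presupposes an AE already on the form. The words on relatedness keep some meaning, because 8.2.1.1 gives the example of a lab abnormality unrelated to the study procedure. The SUSAR text in 8.2.6 does not rebut this, since it is itself built on SAEs.

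This reading is arguable, but it is not stated anywhere and does not fit 8.4. That section makes pregnancy-related events SAEs without any procedure or lab condition. It could be taken as a self-contained addition with its own form, which would shrink the conflict but leave 8.3 without the exception it then needs.

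Two further objections stand in part. Section 8.2.5 defers SAE procedures to the Safety Management Plan, which may have settled practice at the sites; it would not show a reader of the SAP tables which rule applied. And a Deaths row of 0 beside deaths in the survival table is what a deliberately restricted AE design could produce. That is a reason to label the row.

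A reader might also infer that serious events were in fact lost, or that deaths go uncounted. The documents support neither. They show conflicting instructions, not what sites did, and deaths are collected separately.

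**Conclusion.** The conflict in the text is real, and confidence in that is high. The wide rule (8.2.5, 8.4) and the narrow rule (5.1, footnote 7, 8.2 with 8.3, 11.7.1, SAP 2.1) cannot both be followed for a serious event outside the narrow set, unless an unwritten reading is adopted that still leaves the pregnancy SAEs unexplained. Whether any event was omitted is unknown and depends on site practice and on the unseen Safety Management Plan.

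The severity is minor. Graft survival, all-cause patient survival, comorbidity and the other listed endpoints do not draw on AE records. AE incidence is not a listed endpoint, and the study is descriptive with no hypothesis test. What is at risk is the completeness and interpretability of the AE-based outputs. It would be too narrow to infer that only the SAE and Deaths rows are touched, because the same event would also drop out of the all-AE counts, the SOC and PT table and the general listings.

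This review does not say which capture rule should prevail.

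**What to change.** 1. Reconcile Protocol 5.1, 5.2 footnote 7, 8.2, 8.3 and 11.7.1, and SAP 2.1 footnote 7, with 8.2.5 and 8.4 into one capture rule that addresses SAEs explicitly.
2. In SAP 4.5.1, require the rule that applied to be stated on Tables 14.3.16 and 14.3.17 and Listings 16.3.1 to 16.3.5.
3. Footnote the Deaths row of Table 14.3.16 to Table 14.2.3 and Listing 16.2.6.6 as the complete source of deaths.
4. If data collection has ended, check SAE records against the survival and comorbidity records and report discrepancies in the CSR.

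The planned last visit was Q3 2022 (synopsis) or Q4 2022 (Protocol 3.2), and SAP version 2.0 is dated 04 APR 2023. A protocol or CRF change may therefore come too late to alter what was collected, and items 2 to 4 are then the practical remedy. The cost is SAP wording and footnotes, plus a small record check and some retrospective queries for at most 46 subjects. Recorded SAEs must already be source verified under Protocol 9.3.
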